1 CLINICAL PROTOCOL SYNOPSIS

Protocol Title: A Phase 1, Multicentre, Open-Label Study to Evaluate the Pharmacokinetics, Safety, and Tolerability of a Single IV Dose of Rezafungin Acetate in Paediatric Subjects from Birth to <18 Years of Age, Receiving Systemic Antifungals as Prophylaxis for Invasive Fungal Infection or to Treat a Suspected or Confirmed Fungal Infection

Protocol Number: MR907-1501

Study Phase: 1

Sponsor: Mundipharma Research Ltd.

Study Rationale: This study will assess the pharmacokinetics (PK), safety, and tolerability of a single intravenous (IV) dose of rezafungin in paediatric subjects from birth to <18 years who are receiving concomitant systemic antifungals as clinically indicated.

Objectives and Endpoints:

Objectives	Endpoints
Primary	
To evaluate the pharmacokinetics (PK) of a single IV dose of rezafungin in paediatric subjects from birth to <18 years, receiving concomitant systemic antifungals as prophylaxis for invasive fungal infection (IFI) or to treat a suspected or confirmed fungal infection	Parts 1 and 2: The following PK parameters will be assessed: C_{max} , T_{max} , AUC_{0-t} , $AUC_{0-\infty}$, CL , V_{ss} , V_z , $t_{1/2}$ Part 3: Rezafungin plasma concentrations
Secondary	The safety evaluation will be based on clinical review of the following parameters: 
Incidence of treatment-emergent adverse events (TEAEs)Clinical laboratory evaluations (including haematology, blood chemistry and urinalysis)Vital signs12-lead electrocardiograms (ECGs): clinically significant abnormalitiesPhysical examination findings

Number of Subjects and Key Inclusion/Exclusion Criteria:

It is planned to enrol 32 subjects (up to a maximum of 40 subjects [10 per age group] to achieve 32 subjects evaluable for primary analysis).

Eligible subjects will be enrolled into one of the following 4 age groups (8 patients planned per age group):

- Group 1 (12 to <18 years): 8 subjects
- Group 2 (6 to <12 years): 8 subjects
- Group 3 (2 to <6 years): 8 subjects
- Group 4 (birth to <2 years): 8 subjects

Subjects who are withdrawn from the study before completing all PK sampling may be replaced (up to 2 replacement subjects per group is allowed).

Key Inclusion Criteria

Male or female paediatric subjects from birth to <18 years of age who are receiving concomitant systemic antifungals (oral or IV) as prophylaxis for invasive fungal infection (IFI) or to treat a suspected or confirmed fungal infection.

Key Exclusion Criteria

History of anaphylaxis, hypersensitivity, or any serious reaction to the echinocandin class of antifungals and/or excipients of this formulation; Previous or current medical conditions of severe ataxia, persistent tremors, intracranial haemorrhage or neuropathy, or a diagnosis of epilepsy, multiple sclerosis, or a movement disorder (including, but not limited to, cerebral palsy and muscular dystrophy); Subjects with impaired renal or hepatic functions (alanine aminotransferase or aspartate aminotransferase >3 times the upper limit of normal, conjugated bilirubin >24 µmol/L [1.4 mg/dL], serum creatinine >177 µmol/L [2 mg/dL], or receiving renal replacement therapy); Subjects with intestinal hypoxia, ischaemia, necrosis, or necrotising enterocolitis; Subject status is unstable (e.g., with sepsis or disseminated intravascular coagulation), and subject is unlikely to complete required study procedures; Participation in another interventional treatment trial with an investigational agent or presence of an investigational device at the time of informed consent or within 28 days preceding the informed consent.

Summary of Study Design:

This is a Phase 1, multicentre, open-label, single-dose study. The study will be conducted at approximately 10 sites across at least 3 countries in Europe.

The study will be conducted in 3 parts:

- Part 1 will include subjects aged 12 to <18 years (Group 1)
- Part 2 will include subjects aged 6 to <12 years (Group 2), and subjects aged 2 to <6 years (Group 3).

- Part 3 will include subjects from birth to <2 years (Group 4)

The study design for the 3 parts is similar and comprises a Screening (pre-treatment) period from Day -3 to Day -1, Dosing on Day 1 (single IV infusion of rezafungin) followed by multiple PK sampling, and a Follow-up visit on Day 30 (\pm 5 days) (Figure 1, Table 1, Table 2). PK sampling will be performed at specified timepoints for each group.

Part 1: Subjects in Group 1 (12 to <18 years) will be dosed first. For this group, the formulation to be used will be same as the one used in the adult clinical trials at a dose of 3 mg/kg (not to exceed a total dose of 200 mg). PK sampling will be performed at the following 5 timepoints: at end-of-infusion \pm 15 minutes, and thereafter between 3 and 4 hours after start of the infusion, between 6 and 8 hours after start of the infusion, at 48 hours (\pm 4 hours) after start of the infusion (Day 3), and at 168 hours (\pm 12 hours) after start of the infusion (Day 8). The exact date and time of the PK samples must be recorded.

An interim review of safety and PK data will be conducted by the Data Safety Monitoring Board (DSMB) after completion of Group 1. The data will be reviewed by the DSMB to ensure that exposure achieved in the subjects from this group is safe and well tolerated. This will allow for a decision to proceed to Part 2.

In parallel to this study a formulation development programme is being undertaken to identify a paediatric specific formulation for use in subjects <12 years of age. Once the paediatric formulation is available for use, after completion of Part 1, the study will be paused and a substantial amendment will be submitted to enable use of the paediatric formulation in Part 2 and Part 3 (for dosing in subjects <12 years of age).

Part 2: Enrolment for Group 2 and Group 3 will commence after safety has been confirmed by the DSMB and the paediatric formulation has been identified and ready to be used. The planned dose in these age groups is 4 mg/kg (not to exceed a total dose of 200 mg). The PK sampling timepoints for Part 2 will be the same as that dose for Part 1: at endofinfusion \pm 15 minutes, and thereafter between 3 and 4 hours after start of the infusion, between 6 and 8 hours after start of the infusion, at 48 hours (\pm 4 hours) after start of the infusion (Day 3), and at 168 hours (\pm 12 hours) after start of the infusion (Day 8). The dose and PK sampling timepoints may be adjusted as appropriate after assessment of the PK and safety data of Part 1.

A second interim review of safety and PK data will be performed when data from 50% of the subjects enrolled in Part 2 (Group 2 and Group 3) are available. The dose and PK sampling timepoints may be adjusted as appropriate after review of the PK and safety data (DSMB review 2). After completion of Groups 2 and 3; there will be another interim DSMB review (DSMB review 3) of the safety, tolerability, and PK data from the subjects in Groups 1, 2, and 3 (all subjects in Part 1 and Part 2).

A series of juvenile animal toxicity studies will be conducted in parallel with this PK study to investigate the effect of rezafungin on the growing and developing nervous system. Enrolment for Group 4 will not start until the juvenile animal toxicity studies are completed,

Formatte
Color(RG)
Formatte
Custom C
grammar

the animal safety data have been reviewed, and the safety and tolerability from the preceding parts have been confirmed by the DSMB.

Part 3: Subjects from birth to <2 years (Group 4) will be enrolled in Part 3. The planned dose for this age group is 5 mg/kg. Due to blood volume restriction, PK sampling will be done at only 3 timepoints for Group 4: at the end of infusion (\pm 15 minutes), at 24 hours (\pm 4 hours) after start of infusion, and at 168 hours (\pm 12 hours) after start of infusion. A maximum total of 1 mL of blood will be collected for PK sampling. The dose, PK sampling timepoints, extent of safety laboratory data required, and length of the Follow-up period may be adjusted as appropriate after review of the PK and safety data from Part 1 and Part 2 (DSMB review 3).

Investigational Medicinal Product: Rezafungin acetate (MR907)

Rezafungin is a sterile product of lyophilised powder for reconstitution with sterile water for injection prior to dilution into infusion bags containing normal saline, half-normal saline, or 5% dextrose. Each single-dose vial contains rezafungin acetate (200 mg of active rezafungin).

Dose: The dose for Group 1 is 3 mg/kg (not to exceed a total dose of 200 mg). The planned dose for both Group 2 and Group 3 is 4 mg/kg (not to exceed a total dose of 200 mg), and for Group 4, the planned dose is 5 mg/kg. However, the doses for Groups 2, 3, and 4 will be confirmed after a review of the interim PK and safety data from the preceding part(s) by the DSMB (DSMB review 1 and review 3). The dose may be adjusted as appropriate after the review.

Mode of administration: IV infusion over 2 hours (\pm 5 minutes).

Reference Product: Not applicable

Treatment Duration: This is a single-dose study. Subjects will receive a single IV infusion of rezafungin over a period of 2 hours (\pm 5 minutes).

Statistical Methods: In general, continuous data will be summarised by group using the descriptive statistics. Categorical data will be summarised by group as the number and percentage of subjects in each category.

Baseline is defined as the last value prior to the IV infusion of rezafungin (Screening).

Sample Size: No formal sample size calculation was performed. It is estimated that at least 8 subjects per age range will enable estimation of rezafungin PK in subjects from birth to <18 years of age.

Data Analyses:

Pharmacokinetic analysis:

The following PK parameters will be derived for subjects in Groups 1 to 3 only:

- C_{\max} Maximum observed plasma concentration
- t_{\max} Time at which the maximum plasma concentration was observed
- AUC_{0-t} Area under the plasma concentration-time curve from time 0 to the time of the last quantifiable concentration
- $AUC_{0-\infty}$ Area under the plasma concentration-time curve from time 0 extrapolated to infinity
- $t_{1/2}$ Terminal elimination half-life
- λ_z Terminal elimination rate constant
- CL Total clearance
- V_{ss} Volume of distribution at steady-state
- V_z Apparent volume of distribution during the terminal phase

For subjects in Group 4, the plasma concentrations of rezafungin will be summarised using descriptive statistics.

All subjects who receive the single IV infusion of rezafungin and provide at least one blood sample for measurement of rezafungin plasma concentration will be included in the PK analysis set. The PK analysis set will be used for PK analysis.

Individual and mean plasma concentrations of rezafungin at each sampling timepoint will be presented by listings and descriptive statistics including: n, mean, standard deviation (SD), standard error (SE), geometric mean, coefficient of variation expressed as percent (CV%), median, minimum and maximum, as well as quartiles (Q1 and Q3).

All PK parameters will be calculated by non-compartmental analysis and detailed analysis will be included in the Statistical Analysis Plan.

The PK data from all groups may also be analysed using nonlinear mixed-effects modelling. Any PK modelling will be subject to a separate analysis plan and will be reported separately from the clinical study report for this study.

Safety Analysis

The Safety Analysis Set (i.e., all subjects who have received any amount of rezafungin) will be used for the analysis of safety data.

Safety will be evaluated through treatment-emergent adverse events (TEAEs), serious adverse events (SAEs), adverse events of special interest (AESIs), clinical laboratory, vital signs, electrocardiogram (ECG), and physical examination findings. TEAEs are defined as adverse events (AEs) with an onset on or after administration of the investigational product (IP; rezafungin) until the Follow-up.

Adverse events will be coded using the most recent version of the Medical Dictionary for Regulatory Activities (MedDRA).

The number and percentage of subjects experiencing TEAEs will be summarised by group, severity, and relation to IP. Treatment-emergent adverse events will be summarised by MedDRA System Organ Class and Preferred Term. The number and percentage of subjects reporting at least one TEAE will be summarised for each group (Groups 1, 2, 3, and 4), and overall. All AEs will be listed by subject.

Clinical laboratory data to be summarised include haematology, blood chemistry, and urinalysis. Laboratory data will be converted to International System of Units for reporting and processing purposes. Absolute values and changes from baseline will be presented descriptively. Laboratory data outside the reference ranges will be flagged, and clinical significance of the laboratory value change will be stated. Vital signs and 12-lead ECG data will be summarised by group and listed by subject. The number and percentage of subjects with clinically significant ECG findings will be summarised by group for each time-point. A summary of abnormal physical examination findings by group and scheduled visit (Study day) will be presented.

Interim Analysis

No formal interim analysis is planned for this study.

[figure not shown]
A DSMB has been appointed for this study to monitor the safety. Three interim reviews by the DSMB are planned during the study: The first interim review will be performed after completion of Part 1 (Group 1). The enrolment for Part 2 (Group 2 and Group 3) will commence only after DSMB review of Group 1 data and a decision to go ahead.

A second interim review by the DSMB is planned when data from 50% of the subjects enrolled in Part 2 are available.

[figure not shown]
A third DSMB review will be performed when Part 2 is completed. Enrolment for Part 3 (Group 4) will not start before review of safety and PK data from Part 1 and Part 2 is complete.

Figure 1 Study Schema

[figure not shown]
Part 1:

Part 2:

Part 3:

DSMB=Data Safety Monitoring Board; IV=intravenous; PK=pharmacokinetic

*Adult formulation; † paediatric formulation; ‡ DSMB review 2 to be held when 50% data from Group 2 and Group 3 are available; # Interim DSMB review 3: Interim review of safety and PK data of all subjects from Part 1 and Part 2 (Groups 1, 2 and 3).

Table 1 Schedule of Assessments for Part 1 (Group 1: 12 to <18 Years) and Part 2 (Group 2: 6 to <12 Years; and Group 3: 2 to <6 Years)

Study Period	Screening	Dosing		PK Sampling Postdose					Follow-up / ET ^a
Study Day	Day -3 to Day -1	Day 1		Day 1			Day 3	Day 8	Day 30 ± 5 Days
Procedure		Predose	Single IV infusion of rezafungin	end-of-infusion ± 15 mins	Between 3 and 4 hrs after start of infusion	Between 6 and 8 hrs after start of infusion	48 hrs ± 4 hrs after start of infusion	168 hrs ± 12 hrs after start of infusion	
Informed consent/assent for minors ^b	x								
Assess inclusion/exclusion criteria	x								
Demography (age, sex, and race)	x								
Baseline characteristics (height, weight, BMI*, and disease characteristics [indication for antifungal prophylaxis/treatment])	x								
Hospitalisation status at Screening (general ward/ICU) ^c	x								
Medical/surgical history and current medical conditions	x								
Prior and concomitant medication use ^d	x	x	x	x	x	x	x	x	x
Physical examination ^e	x	x	x	x	x	x	x	x	x

Study Period	Screening	Dosing		PK Sampling Postdose					Follow-up / ET ^a
Study Day	Day -3 to Day -1	Day 1		Day 1			Day 3	Day 8	Day 30 ± 5 Days
Procedure		Predose	Single IV infusion of rezafungin	end-of-infusion ± 15 mins	Between 3 and 4 hrs after start of infusion	Between 6 and 8 hrs after start of infusion	48 hrs ± 4 hrs after start of infusion	168 hrs ± 12 hrs after start of infusion	
Vital signs (temperature, pulse rate, respiratory rate, and blood pressure) ^f	x	x	x ^f	x ^f	x	x	x	x	x
Clinical laboratory tests (haematology, biochemistry, urinalysis) ^g	x								x
Urine pregnancy test for postmenarchal females	x								x
12-lead ECG ^h	x				x				
IP administration ⁱ			x						
Continuous vital sign and ECG monitoring (only during IP infusion) ^j			x						
PK Sampling (venous or arterial samples) ^k				x	x	x	x	x	
AE/SAE monitoring			x	x	x	x	x	x	x
Infusion-related reaction monitoring (collected as AEs)			x	x	x	x			

AE=adverse event; BMI=body mass index; ECG=electrocardiogram; ET=early termination; ICU=intensive care unit; IP=investigational product; IV= intravenous; PK=pharmacokinetics; SAE=serious AE.

Note: When coinciding with each other, ECGs, vital signs, and pharmacokinetic blood collections should be performed in said order.

* BMI=kg/m² where kg is a subject's weight in kilograms and m² is their height in metres squared ([Appendix 6](#)).

- a. ET assessments can be performed at the time of discontinuation. In case of ET, the reason for discontinuation must be documented.
- b. Written parental (or appropriate legal representative) informed consent and/or age-appropriate assent/consent.
- c. Record whether the subject is in the general ward or ICU. If the subject is in the ICU, record the Paediatric Index of Mortality 2 (PIM2) variables ([Appendix 7](#)).
- d. All medication taken up to 7 days prior to the informed consent, medication ongoing after the informed consent, and all medication given to the subjects during the study until Follow-up (Day 30 ± 5 days) must be recorded.
- e. A complete physical examination is to be performed at Screening and Follow-up. At all other time points, a brief targeted examination is to be performed as clinically indicated, driven by the subject's symptoms and signs. A complete and brief targeted physical examination will include, at a minimum, assessments of the cardiovascular, respiratory, gastrointestinal, and central and peripheral neurological systems.
- f. Vital signs will be taken after subject is sitting or supine for at least 5 minutes and will include temperature, pulse rate, respiratory rate, and blood pressure. On the day of dosing (Day 1) vital signs will be taken predose, 15-30 minutes after the start of IP infusion, and 30-60 minutes after the completion of IP infusion.
- g. Clinical laboratory tests (haematology, biochemistry, urinalysis): The following tests will be performed at Screening and at Follow-up: Complete blood count, alkaline phosphatase (ALP), blood urea nitrogen (BUN), alanine aminotransferase (ALT), aspartate aminotransferase (AST), total and conjugated bilirubin, creatinine, total protein and albumin, glucose (fasting or non-fasting), potassium, sodium, calcium (see [Appendix 2](#) for details).
- h. 12-lead ECG: at Screening and between 3 and 4 hours after start of IP infusion on Day 1.
- i. The IP will be administered as a single IV infusion over a period of 2 hours (± 5 minutes). The formulation used for Group 1 will be same as the one used in the adult clinical trials. For Group 2 and Group 3, a paediatric specific formulation that is currently under development will be used.
- j. Continuous vital sign and ECG monitoring will begin with start of IP infusion until completion of infusion.
- k. PK blood samples will be collected at the following 5 timepoints: at end-of-infusion ± 15 minutes, then between 3 and 4 hours after start of infusion, between 6 and 8 hours after start of infusion, at 48 hours (± 4 hours) after start of infusion (Day 3), and at 168 hours (± 12 hours) after start of infusion (Day 8). In cases where a subject is discontinued before all PK samples have been collected (Day 8), a last PK sample may be collected at the time of discontinuation if the subject and/or his/her parent(s)/legally authorised representative consents. The exact date and time of the PK samples must be recorded.

Table 2 Schedule of Assessments for Part 3 (Group 4: birth to <2 Years)

Study Period	Screening	Dosing		PK Sampling Postdose			Follow-up / ET ^a
Study Day	Day -3 to Day -1	Day 1		Day 1	Day 2	Day 8	Day 30 ± 5 Days
Procedure		Predose	Single IV infusion of rezafungin	end-of-infusion ± 15 mins	24 hrs ± 4 hrs after start of infusion	168 hrs ± 12 hrs after start of infusion	
Informed consent (parental consent/LAR) ^b	x						
Assess inclusion/exclusion criteria	x						
Demographics (age, sex, race, gestational age, and birth weight)	x						
Baseline characteristics (height, weight, and disease characteristics [indication for antifungal prophylaxis/treatment])	x						
Hospitalisation status at screening (general ward/ICU) ^c	x						
Medical/surgical history and current medical conditions	x						
Prior and concomitant medication use ^d	x	x	x	x	x	x	x
Physical examination ^e	x	x	x	x	x	x	x
Vital signs (temperature, pulse rate, respiratory rate, and blood pressure) ^f	x	x	x ^f	x ^f	x	x	x

Study Period	Screening	Dosing		PK Sampling Postdose			Follow-up / ET ^a
Study Day	Day -3 to Day -1	Day 1		Day 1	Day 2	Day 8	Day 30 ± 5 Days
Procedure		Predose	Single IV infusion of rezafungin	end-of-infusion ± 15 mins	24 hrs ± 4 hrs after start of infusion	168 hrs ± 12 hrs after start of infusion	
Clinical laboratory tests (haematology, biochemistry, urinalysis) ^g	x						x
12-lead ECG ^h	x				x		
IP administration ⁱ			x				
Continuous vital sign and ECG monitoring (only during IP infusion) ^j			x				
PK Sampling (venous or arterial samples) ^k				x	x	x	
AE/SAE monitoring			x	x	x	x	x
Infusion-related reaction monitoring (collected as AEs)			x	x	x		

AE=adverse event; ECG=electrocardiogram; ET=early termination; ICU=intensive care unit; IP=investigational product; IV= intravenous; LAR=legally authorised representative; PK=pharmacokinetics; SAE=serious AE.

Note: When coinciding with each other, ECGs, vital signs, and pharmacokinetic blood collections should be performed in said order.

- ET assessments can be performed at the time of discontinuation. In case of ET, the reason for discontinuation must be documented.
- Written parental (or appropriate legal representative) informed consent.
- Record whether the subject is in the general ward or ICU. If the subject is in the ICU, record the Paediatric Index of Mortality 2 (PIM2) variables ([Appendix 7](#))
- All medication taken up to 7 days prior to the informed consent, medication ongoing after the informed consent, and all medication given to the subjects during the study until Follow-up (Day 30 ± 5 days) must be recorded.
- A complete physical examination is to be performed at Screening and Follow-up. At all other time points, a brief targeted examination is to be performed as clinically indicated, driven by the subject's symptoms and signs. A complete and brief targeted physical examination will include, at a minimum, assessments of the cardiovascular, respiratory, gastrointestinal, and central and peripheral neurological systems.

- f. Vital signs will be taken in supine position and will include temperature, pulse rate, respiratory rate, and blood pressure. On the day of dosing (Day 1) vital signs will be taken predose, 15-30 minutes after the start of IP infusion, and 30-60 minutes after the completion of IP infusion.
- g. Clinical laboratory tests (haematology, biochemistry, urinalysis): The following tests will be performed at Screening and at Follow-up: Complete blood count, alkaline phosphatase (ALP), blood urea nitrogen (BUN), alanine aminotransferase (ALT), aspartate aminotransferase (AST), total and conjugated bilirubin, creatinine, total protein and albumin, glucose (fasting or non-fasting), potassium, sodium, calcium (see [Appendix 2](#) for details). Glucose can be measured by point-of-care testing to minimise the blood volume taken for the clinical laboratory tests if the point-of-care glucose meter is calibrated regularly as per the site's standard operating procedure.
- h. 12-lead ECG: at Screening and at 24 ± 4 hours after start of IP infusion (Day 2).
- i. The IP will be administered as a single IV infusion over a period of 2 hours (± 5 minutes).
- j. Continuous vital sign and ECG monitoring will begin with start of IP infusion until completion of infusion.
- k. PK blood samples will be collected at the following 3 timepoints: at end-of-infusion ± 15 minutes, at 24 hours ± 4 hours (Day 2) after start of infusion, and at 168 hours ± 12 hours (Day 8) after start of infusion. In cases where a subject is discontinued before all PK samples have been collected (Day 8), a last PK sample may be collected at the time of discontinuation if the subject and/or his/her parent(s)/LAR consents. The exact date and time of the PK samples must be recorded. A maximum total of 1 mL of blood will be taken for PK sampling.

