7.1 Study Treatment Administered

This is an open-label study and all subjects will receive a single IV infusion of rezafungin over 2 hours (\pm 5 minutes).

Part 1 (Group 1 – 12 to <18 years of age)

The IP formulation used for Group 1 will be same as the one used in the adult clinical trials. Dose for Group 1 will be 3 mg/kg (not to exceed a total dose of 200 mg).

Part 2 (Group 2 – 6 to <12 years and Group 3 – 2 to <6 years of age) and Part 3 (Group 4 – from birth to <2 years of age)

In parallel to this clinical study, a formulation development programme is being undertaken to identify a lower strength paediatric specific formulation with an appropriate PS80 level for use in subjects <12 years of age. When an adequate paediatric formulation is identified, after the completion of Group 1, the study will be paused and a substantial amendment will be submitted to enable the paediatric formulation to be used in the subjects in Groups 2, 3, and 4.

The planned dose for Group 2 and Group 3 is 4 mg/kg (not to exceed a total dose of 200 mg) and the planned dose for Group 4 is 5 mg/kg; however, the doses will be confirmed after assessment of the interim PK and safety data. The doses may be adjusted as appropriate.

Table 3 Study Treatment Administered

Study Treatment	Test Product
Study Treatment Name	Rezafungin acetate (MR907)
Treatment Description	
Part 1: Rezafungin is a sterile product of lyophilised powder for reconstitution with sterile water for injection prior to dilution into infusion bags containing normal saline, half-normal saline, or 5% dextrose. Each single-dose vial contains rezafungin acetate (200 mg of active rezafungin) and excipients, including polysorbate 80 (450 mg), mannitol (500 mg), and histidine (47 mg). The formulation may contain hydrochloric acid and/or sodium hydroxide as needed for pH adjustment.
 
After reconstitution of the lyophilised powder with water for injection, the reconstituted solution should be immediately diluted into infusion bags containing normal saline, half-normal saline or 5% dextrose.
 
Part 2 and Part 3: Formulation information will be included when available.

Formulation	Powder for concentration for solution for infusion (for Part 1). Formulation for Part 2 and Part 3 will be included when available.
Unit Dose Strength	200 mg/vial (for Part 1)

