10.4.3 Primary Endpoints Analyses

For Parts 1 and 2, PK parameters are primary endpoints for this study. The following PK parameters will be determined: C_{max} , T_{max} , AUC_{0-t} , $AUC_{0-\infty}$, CL, V_{ss} , V_z , and $t_{1/2}$.

For Part 3, as only three plasma concentrations will be determined from each subject, there will not be sufficient data to determine PK parameters. Therefore, the plasma concentrations will be listed and summarised using descriptive statistics.

For details see Section [10.5](#).

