10.5.2 Pharmacokinetic Parameters

For Parts 1 and 2, the following PK parameters will be determined from the rezafungin concentration-time data using non-compartmental methods (Phoenix WinNonlin®, Build 8.0.0.3176 or higher, Certara USA, Inc., Princeton, New Jersey, US) and actual sampling times:

C_{\max}	Maximum observed plasma concentration
t_{\max}	Time at which the maximum plasma concentration was observed
AUC_{0-t}	Area under the plasma concentration-time curve from time 0 to the time of the last quantifiable concentration
$AUC_{0-\infty}$	Area under the plasma concentration-time curve from time 0 extrapolated to infinity
$t_{1/2}$	Terminal elimination half-life
λ_z	Terminal elimination rate constant
CL	Total clearance
V_{ss}	Volume of distribution at steady-state
V_z	Apparent volume of distribution during the terminal phase

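### The ±15-minute window lets the first PK sample be drawn during the infusion; off-time draws can only understate the peak, mainly affecting Group 4's end-of-infusion concentration

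*Combined protocol and SAP*

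**What the plan says.** Infusion: under Section 7.1, "all subjects will receive a single IV infusion of rezafungin over 2 hours", with a tolerance of ±5 minutes.

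First sample, Groups 1–3 (Table 1, footnote k): "PK blood samples will be collected at the following 5 timepoints: at end-of-infusion ± 15 minutes". The next two are "then between 3 and 4 hours after start of infusion, between 6 and 8 hours after start of infusion", followed by samples at 48 and 168 hours.

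First sample, Group 4 (Table 2, footnote k): "PK blood samples will be collected at the following 3 timepoints: at end-of-infusion ± 15 minutes". The next is at 24 ± 4 hours and the last at 168 hours.

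The symmetric window recurs in the synopsis and Sections 5.1, 5.1.4, 9.3.2 and 9.3.3. Tables 1 and 2 place the sample under a postdose heading, but nothing in the text bars a draw while the infusion is running.

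Endpoints: Section 10.4.3 states "For Parts 1 and 2, PK parameters are primary endpoints for this study", and Cmax and Tmax are among them. Section 10.5.2 defines Cmax as "Maximum observed plasma concentration". Group 4 has no Cmax; its primary endpoint is the plasma concentrations, listed and summarised. Section 10.5.1 summarises concentrations by sampling timepoint. Exact sample times are recorded, and the non-compartmental analysis uses actual times.

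**The concern.** Under a constant-rate infusion with first-order elimination (the structure given in Section 5.3), plasma concentration rises until the infusion stops and then falls. A timing error on either side lowers the measured value, so errors do not cancel across subjects as they would at a point on a straight decline.

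The planned analysis does not undo this. Actual times give a correct AUC and an honest tmax, but Cmax is simply the largest value observed. A summary by nominal timepoint takes each concentration as it stands. No rule flags a draw made before the infusion ended. Such a draw can also produce a tmax that falls within the infusion.

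At stake are Cmax and tmax in Groups 1–3, which the DSMB sees when it judges whether exposure is safe before younger children are dosed, and one of only three primary values per child in Group 4, with 8 children planned. Differences between sites in when they draw within the window would also add spread in groups of 8.

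**Working it through.** **Inputs from the protocol.** Infusion 120 min (115–125); window ±15 min; adult clearance about 0.2 L/h, volume about 40 L, half-life 5 to 6 days (Section 3.3); three-compartment model with no parameter values (Section 5.3).

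**Check of the protocol's own figures.** Half-life = ln 2 × 40 / 0.2 = 138.6 h = 5.78 days, within the stated range. Polysorbate 80 rate at 3 mg/kg over 120 min = 3 × (450/200) / 120 = 0.05625 mg/kg/min, against 0.0563 in Section 7.2. A constant 120-minute rate is therefore what the protocol assumes.

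**One compartment.** k = 0.2/40 = 0.005 per hour, T = 2 h. Relative to the value at T:
- 15 min early: (1 − e^(−0.005×1.75)) / (1 − e^(−0.005×2)) = 0.876. For 115- and 125-minute infusions: 0.870 and 0.881.
- 15 min late: e^(−0.005×0.25) = 0.999.
- At 3 h and 4 h: e^(−0.005) = 0.995 and e^(−0.010) = 0.990.
- At 24 h: e^(−0.005×22) = 0.896.

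**Two compartments (assumed distribution).** Total volume 40 L, clearance 0.2 L/h, central share 20, 25, 50 or 75%, distribution half-life 0.1, 0.25, 0.5, 1, 2, 4 or 8 h: 28 scenarios. C(t) = Σ (R·Aᵢ/λᵢ)(1 − e^(−λᵢ·min(t,T)))·e^(−λᵢ·max(t−T,0)), where R is the infusion rate and Aᵢ, λᵢ are the coefficients and rates of the two exponential phases.

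| Share of true peak (120-min infusion) | One compartment | Two compartments |
|---|---|---|
| Single draw at −15 min | 87.6% | 87.8–93.2% |
| Single draw at +15 min | 99.9% | 78.7–99.3% |
| Single draw at +5 min | almost 100% | 90.0–99.8% |
| Sample at 24 h | 89.6% | 17.9–87.5% |
| First sample, mean over ±15 min | 96.8% | 91.6–96.8% |
| Larger of first and 3–4 h sample, mean over ±15 min | 99.6% | 91.6–98.3% |
| First sample, mean over 0 to +15 min | 99.9% | 88.1–99.7% |
| First sample, mean over 0 to +5 min | almost 100% | 94.6–99.9% |

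Means take draws spread evenly over the window.

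**Groups 1–3.** Cmax is the largest of five samples, so the 3–4 h sample can stand in for a low first one. After a draw at −15 min, Cmax is at most about 1% low with one compartment and 2.6–11.7% low with two. Averaged over the window, the loss is 0.4% and about 2–8% respectively.

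**Group 4.** The 24 h sample is seldom high enough to stand in, and a summary by timepoint would not use it that way. The end-of-infusion value carries the full 7–13% of an early draw, or about 3–8% on average.

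**Which change helps.** A 0 to +5 min target gave a higher mean than ±15 min in all 29 scenarios (28 plus the one-compartment case). Moving to 0 to +15 min was better in only 21 of 29: with fast distribution and a small central volume, late draws lose more than early ones.

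**Excluding early draws.** With a 25% central share and distribution half-life of 0.25–1 h, a −15 min sample is at 91–93% of peak. Excluding it leaves the 3–4 h sample as Cmax, at 52–68%.

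**The case against.** The strongest reply is that the rule aims at the end of infusion and only permits an early draw. A draw on time has no error, and the postdose heading suggests that sites should wait. For Groups 1–3 the 3–4 h sample is a real safeguard. Exact times are recorded, and Section 5.2 says that the sparse data will feed a population PK model, which uses actual times and handles a draw during the infusion without bias. The protocol sets no Cmax threshold or exposure-matching criterion that an error of this size would cross.

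Most of this stands as a limit on size. It does not remove the point. The heading and the window contradict each other, and the window is what appears in every section. Section 10.7 makes the modelling optional and separately reported, so it does not protect the primary endpoints in the study report.

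A reader might infer that the rule biases Cmax by some 12%. The documents do not support that: the figure is one sample's shortfall for the earliest permitted draw, whereas Cmax is the maximum of five samples. Nor can it be carried over to a Group 4 Cmax, because Group 4 has none. A reader might also infer that DSMB decisions would be distorted. No decision rule in the protocol depends on Cmax, and all three planned reviews precede Group 4, where the effect is largest.

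**Conclusion.** The point holds as a moderate, one-directional weakness that is cheap to remove. An early draw understates that sample by about 7–13%. This depends little on the unknown parameters, because it is bounded near 15/120 = 12.5% (15/115 = 13.0% for the shortest permitted infusion). A late draw loses 0 to about 20%, and that range rests wholly on assumed distribution values. The effect is greatest for Group 4's end-of-infusion concentration. In Groups 1–3 the average loss in Cmax lies between under 1% (one compartment) and about 2–8% (with a distribution phase). The sponsor's three-compartment model makes the one-compartment limit less likely, but the protocol gives nothing to place the answer within the range.

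Assumptions: linear kinetics; a constant, uninterrupted rate (Section 7.6 allows slowing or interruption after a reaction); adult clearance and volume; draws spread evenly for the averages. How sites would actually use the window is not known.

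**What to change.** In the substantial amendment already planned before Part 2, change Tables 1 and 2, the synopsis and Sections 5.1, 5.1.4, 9.3.2 and 9.3.3 to read: *immediately after the infusion has stopped, target 0 to +5 minutes; not before the infusion has stopped*. This also reconciles the window with the postdose heading. Keep later draws, with their recorded times.

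In the SAP, which is to be finalised before database lock:
- Flag any draw made before the actual stop time, including in Group 1. Confirm that the eCRF captures that stop time; Section 7.5 mentions only the date and time of the infusion, in source documents.
- Do not exclude flagged draws from Cmax in the main summary, because the replacement sample can be much lower.
- Show Cmax and the Group 4 end-of-infusion summary with and without flagged draws.

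Cost: wording, one flag and one extra summary, with no added blood, sample or visit. The downside is a tighter draw time for site staff. Some loss remains: in the most extreme scenario tried, a draw at +5 minutes is still 10% low.
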